## **STUDY Protocol Sub-study 2: Interventions focusing on nutrition and physical activities for overweight and obese older adults in nursing homes "IFEBO" (A feasibility study)**

**Authors:** [name], [name], [name], [name] and [name]

- 1. Title for the project:** Interventions focusing on nutrition and physical activities for overweight and obese older adults in nursing homes "IFEBO"
- 2. Purpose:** The overall purpose is to investigate how muscle function and care-related quality of life can be maintained or improved through nutrition and physical activity interventions in older adults in nursing homes. Older adults with the combination of both overweight and T2D have a special focus in the sub-study, as the two conditions together increased the demands on the nutritional intervention.
  - a. Specific objectives:**
    - What components of existing practice should be included in interventions focusing on nutrition and physical activities?
    - What interventions are feasible in practice?
    - Does the screening model identify the older adults in need of a nutrition and physical activity intervention?

The project's hypothesis is that the older adults with Ow/O may be malnourished and may benefit from interventions that combine nutrition and physical activities.

### **b. Short literature review and bibliography**

The aging population is increasing both globally (1) and nationally (2). Concurrent with the generally rapidly increasing incidence of overweight (3), a large number of older people risk facing a number of health problems associated with overweight and obesity (Ow/O) (1). Ageing related to malnutrition or undernutrition have received a lot of attention. However, overnutrition described as Ow/O is also classified as a nutritional disorder or a nutrition related condition, in the same term as malnutrition (18).

Today, all older adults in Danish nursing homes are offered an enriched diet type for malnourished older adults, focused on energy dense snacks and a high fat percentage (4). This is not necessarily an appropriate diet, but it is unknown which nutritional interventions that are effective in maintaining/ improving physical functioning, independency and quality of life. One of the concerns is that many older adults with Ow/O may have loss of muscle mass, which can worsen with weight loss (5–9), if this is not taken into account in the nutritional intervention. There is therefore a clear need to develop targeted interventions for older adults with Ow/O that can maintain or improve physical functioning and quality of life under Danish conditions with the Danish dietary tradition.

However, a literature review of interventions within the last 10 years shows that none of the interventions are aimed at healthy older adults  $\geq 65$  years with a  $\text{BMI} \geq 25\text{kg/m}^2$  and good physical functioning. Instead, interventions targeted older adults with Ow/O with either low physical functioning or chronic diseases. These interventions show that older adults can lose weight, but without significant positive effects on functioning and quality of life (10–16). However, interventions aimed at the target group for this project, which has both reduced muscle function and chronic disease, that nutrition and physical activity interventions have a positive effect on physical functioning (17–22) and quality of life (18,21,22). The interventions in the studies contain complex nutrition and exercise interventions, and the differences in the

intervention descriptions and target groups make it difficult to compare and point to safe and effective interventions.

In addition, the studies show that there is no difference between whether the nutrition intervention applies weight loss or weight maintenance interventions (10–20,22,23), but that the intervention itself has an effect, even when the weight is maintained.

However, the above literature review has confirmed that there are older people with Ow/O, especially those with both low physical function and chronic disease, who may benefit from a nutritional intervention, which has led to a proposed screening model (24). The characterization according to the screening model will be performed in sub-study 1, and furthermore adapted to be easy-to-use in a community health care setting.

In sub study 2, on the basis of the screening model (sub study 1), the project, in co-creation with the older adults, the care staff and the project participants, develop and test nutritional interventions that can improve muscle function and quality of life of the target group.

### 3. Methods

#### a. Study design and methods

This pragmatic feasibility cluster randomized controlled intervention study will be performed at six nursing homes in Odsherred City. Participants and care staff from nursing homes in Odsherred City will contribute to the design of this study protocol.

The research group include participants experience from sub study 1. Moreover, the participant's experiences are central during the feasibility state.

#### Sample size calculation:

Initially the power calculation is performed by the individual randomization, calculated on the basis of the 30 secound chair stand test. The starting point is six nursing homes is involved in the study. Approximately 40-50 residents are living in each location and assumable half of them are Ow/O and wants to participate in the project. (n=20). A desired detectable change of 1.3 (39), a P-value <0.05 and a power of 80%. The study has two arms (control and intervention) and the standardized difference in the nursing center incl. intra cluster correlation, SD diff, nursing center = 0.42.  $SD(\text{diff.}, \text{nursing center}) = (SD(\text{diff.}, \text{person}))/\sqrt{n}$ , SD diff, person  $\approx 1.87$  If SD is 1.87 or less, the power will be at least 80% or greater. If there are more than 20 people per. care center power will increase and if there are fewer than 20 people power will decrease. After sub study 1 a more accurate number can be provide, also knowing what is feasible in sub study 2.

Approximately 100 participants will be included and cluster randomized to either 6 month of nutritional and physical intervention or 6 month of usual care (control). A simple random sample without replacement will be selected by a non-project group member using the lottery method. Effects from the intervention will be examined by mixed methods that include both quantitative and qualitative data, as well as action research that focuses on creating development and change in collaboration with participants and care staff at the nursing homes.

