#### All outcome measures

Data are collected at baseline and 6 months (m). The starting point is the same measurements as described in sub-study 1, combined with feasibility in practice.

The data analysis takes into account that not all participants are included in all measurements.

Tabel 1: Data collection in sub study 2

Variable	Method	Baseline	6 m
Age and sex	Journal data	x	
Weight	Calibrated standard weight as part of routinely weighing, Journal data	x	x
Weight, fat%, fat mass (kg), muscle mass (kg), bone mass (kg), BMI, total body water (TBW), TBW%, intracellular water and extracellular water	BIA	x	x
Calf circumference	Measured by non-elastic plastic tape		
Height	Journal data	x	
Height measured	Measured standing or lying	x	
Chronic disease, diagnosis and number	Journal data	x	
Muscle function	30 s CST , gait speed and HGS	x	x
Nutritional risk	EVS	x	x
Quality of Life	ASCOT questionnaire	x	x

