#### **c. Deviations from standard care**

Control group include three nursing homes and participant will follow standard care. The interventions group including three nursing homes will implement the intervention developed on

the basis of new knowledge from sub-study 1, previous studies, practical experiences, the participant's experiences and wishes as well as the staff's experiences and wishes.

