#### **6. Risks, side effects and disadvantages in the short and long term**

In the study, no serious adverse events or risks are expected. All participants participate voluntarily and can withdraw from the study at any time. The research group can withdraw a participant at any time if there is a concern for the participant's well-being. A nurse at each of the nursing homes is included in the project and will be present during all data collection periods. The nurses will be involved immediately if any health issues or concerns about health issues should arise. Data on participants who withdraw will be documented.

This project meets the guidelines of the Declaration of Helsinki II, as well as the guidelines of the Regional Ethics Committee.

The research project has been submitted to the Science Ethics Committees for Region Zealand j.nr.: EMN-2021-07672 and is exempt from the obligation to notify.

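### The 80% power statement counts residents who agree to join and allows nothing for those without a 6-month chair-stand result; at the limiting SD it has almost no slack

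*Protocol*

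**What the plan says.** All of this is in the protocol.

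- **Clusters and arms.** "The starting point is six nursing homes is involved in the study" (Sample size calculation). "Control group include three nursing homes and participant will follow standard care" (section 3c). The other three homes receive the intervention.
- **Residents per home.** With 40-50 residents in each home, "assumable half of them are Ow/O and wants to participate in the project. (n=20").
- **Target.** "A desired detectable change of 1.3 (39), a P-value <0.05 and a power of 80"%, on the 30-second chair stand test.
- **Variability.** The home-level figure is "incl. intra cluster correlation, SD diff, nursing center = 0.42". It is tied to the person-level SD by dividing by the square root of n, which gives about 1.87 for a person.
- **Power statement.** "If SD is 1.87 or less, the power will be at least 80% or greater". The paragraph adds that power rises above 20 people per home and falls below it, and that a more accurate number can follow sub-study 1.
- **Enrolment.** The same section and section 3b both expect about 100 participants in total.
- **Follow-up.** "Data are collected at baseline and 6 months (m"), under All outcome measures, which also notes that not everyone will have every measurement.
- **Losses.** Section 6 lets participants withdraw at any time, lets the research group withdraw them, and says: "Data on participants who withdraw will be documented". Section 12 lets residents decline performance tests, in which case only record data are collected. Section 4 foresees absent results under intention to treat. No section puts a number on any of this.

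**The concern.** When a person-level SD is divided by the square root of n to get the SD of a home mean, n is the number of residents whose outcome enters that mean. The protocol uses the number willing to join. With one test after baseline, a resident who has died, withdrawn or declined the test by 6 months adds no chair-stand outcome, and intention to treat does not supply one. Section 3b mentions continuing inclusion but does not describe it as replacing losses.

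This matters because the power statement is worded as a guarantee, subject to an SD limit, and that limit was set to give just 80% at n = 20. If fewer are tested, a non-significant result carries less information than the protocol suggests. The enrolment figure of about 100 is already below 6 × 20 = 120, so the shortfall exists before anyone is lost.

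**Working it through.** **Inputs from the protocol.** Difference 1.3 stands; significance level 0.05 (sidedness not stated); 3 v 3 homes; home-level SD 0.42; person-level SD 1.87; n = 20 per home; enrolment about 100, so 100/6 = 16.7 per home.

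**Assumed.** A 6-month loss of 5-30%, since the documents give none; and, in step 4 only, a value for the intra-cluster correlation (ICC).

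**1. Reproducing the 80%.** Two-sided t-test on home means, 3 v 3, so 4 degrees of freedom and critical value 2.776.

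- Noncentrality = 1.3 / (SD_home × √(2/3)).
- SD_home = 0.42: 1.3 / (0.42 × 0.8165) = 3.79; power 80.6%.
- SD_home = 1.87/√20 = 0.418: noncentrality 3.81; power 80.9%.

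This matches the protocol. Alternatives do not: a normal approximation on three homes per arm gives 96.6%, individual randomisation with 60 per arm 96.8%, a one-sided t-test 92.4%, and three matched pairs 76.6%.

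**2. How much slack there is.** Exactly 80% power needs SD_home = 0.4233. With SD 1.87 this means n = (1.87/0.4233)² ≈ 19.5, a loss of 0.5/20, or about 2.4%. At 19 per home, power is 79.0%.

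**3. Effect of loss**, with SD_home = 1.87/√n. The largest person-level SD giving 80% power is 0.4233 × √n. The detectable difference at SD 1.87 is 1.3 × 1.87 divided by that SD.

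| Start | Assumed loss | Tested per home | Power | Largest SD for 80% | Detectable difference |
|---|---|---|---|---|---|
| 20 per home | 0% | 20 | 80.9% | 1.89 | 1.28 |
| | 5% | 19 | 79.0% | 1.85 | 1.32 |
| | 10% | 18 | 77.0% | 1.80 | 1.35 |
| | 20% | 16 | 72.3% | 1.69 | 1.44 |
| | 30% | 14 | 66.9% | 1.58 | 1.53 |
| About 100 in all | 0% | 16.7 | 73.9% | 1.73 | 1.41 |
| | 10% | 15.0 | 69.7% | 1.64 | 1.48 |
| | 20% | 13.3 | 64.9% | 1.55 | 1.57 |
| | 30% | 11.7 | 59.4% | 1.45 | 1.68 |

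**4. If the 0.42 already contains between-home variance, as the text says.** Write SD_home² = s² × (ICC + (1 − ICC)/n) and hold SD_home at 0.42 for n = 20. At an assumed ICC of 0.05, s² = 0.1764/0.0975 = 1.809. With 16 tested, SD_home² = 1.809 × (0.05 + 0.95/16) = 0.198, so SD_home = 0.445 and power is 76.2%. With 18 tested it is 78.6%, and with 14 it is 73.3%. The loss costs less than in step 3, but power is still below 80%.

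**The case against.** The strongest reply is that the protocol already hedges. It ties the 80% to 20 people per home, says power falls with fewer, and calls the number provisional until sub-study 1 is done. That is fair as to direction. But it neither sizes the fall nor says that n means residents tested at 6 months, so the update could repeat the same count of joiners.

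A reader might infer that the trial cannot have 80% power even when its SD condition is met. The documents do not support that. The condition covers any SD up to 1.87, and the shortfall arises near that limit: from 20 per home, an SD of 1.80 absorbs 10% loss and 1.69 absorbs 20%. No loss rate is stated either. The analysis is ANCOVA adjusted for baseline, which may help. If 1.87 is the SD of a change score (the protocol does not say clearly), adjustment multiplies the variance by (1 + r)/2, where r is the baseline to follow-up correlation. At an assumed r of 0.6, 16 tested count as 16/0.8 = 20, which restores 80.9%. The power calculation takes no credit for this, and from about 100 enrolled with 10% loss the equivalent is 15/0.8 = 18.75, still short of 19.5.

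Half of 40-50 is 20-25, so 20 is the low end. At 22.5 per home, 10% loss leaves 81.4%. The planned total of about 100 removes that margin.

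A reader might also infer that any positive ICC lowers the step 3 powers further. That follows only if the ICC is added on top of 0.42, against the text. On the text's own premise it softens the effect of loss. Whether 0.42 really contains an ICC, given a formula with no ICC term, is a separate question.

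Finally, this is a feasibility study, and no sum is wrong; an assumption is unstated. Both points limit the weight of the finding. Neither makes the printed power statement hold for the number likely to be tested.

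**Conclusion.** The point holds in a limited form. The statement of at least 80% power at SD 1.87 or less is true only if about 19.5 or more residents per home have a 6-month chair-stand result. The protocol makes no allowance for residents without one, although it foresees them.

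At SD 1.87, power is 77%, 72% and 67% for 10%, 20% and 30% loss from 20 per home. From the enrolment actually planned it is 73.9% before loss and about 70%, 65% and 59% after. These sizes rest on the assumed loss range, an SD at the limit, and a t-test on home means with the SD formula as printed. If the 0.42 contains true between-home variance the fall is smaller (about 76% with 16 tested at an assumed ICC of 0.05), and an SD sufficiently below 1.87 would still give 80%. The fault is a stated power that needs restating; it does not show that the trial must fall short.

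**What to change.** In the Sample size calculation paragraph:

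1. Define n as the residents per home expected to have a 30-second chair-stand result at 6 months.
2. Start from the enrolment actually planned, about 100 in six homes, and state the assumed 6-month loss.
3. Replace the sentence promising at least 80% with the power, the largest SD or the detectable difference at that n. For example, with SD 1.87 and 15 or 13.3 tested per home (10% or 20% loss from about 100): power 70% or 65%, largest SD for 80% power 1.64 or 1.55, detectable difference 1.48 or 1.57 stands.
4. Use the same definition of n in the update after sub-study 1.

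The cost is a rewritten paragraph and a less favourable stated power. Enrolment, staffing and visits stay as planned.

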#### b. The practical implementation, intervention and scope

Six nursing homes in Odsherred City, Region Zealand, Denmark, participate in the project, and estimated 100 older adults is expected to be enrolled in the project. There will be ongoing inclusion.

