## **12. Recruitment of subjects and informed consent**

Recruitment of project participants takes place from Odsherred city's 6 nursing homes. The first step in recruitment takes place by principal investigator orally and in writing informing the nursing homes, care staff, relatives, nursing home councils and the residents of the nursing homes about the project's purpose, content and course. Posters are posted telling about the project. In the next step, (oral information) the principal investigator, the care staff and relatives talk to the residents.

Participant information (written information) is provided for both sub-studies as well as the leaflets "Subjects' rights in a health science research project", and "Before you decide - to be in health science experiments". The written information contains a description of the project, its purpose, method and possible consequences associated with the participants' participation. Participation in the project is voluntary, and the participants have the opportunity, without further justification, to interrupt the collaboration and their participation in the project. In the third step, the residents then have 24 hours to decide whether they want to participate in the project and sign a declaration of consent. During the project period, the participants can obtain further information about the project from the principal investigator. Collection, storage and processing of empirical data is done with the Danish Data Protection Agency's instructions for handling confidential information in research work of an empirical nature.

Participants have the opportunity to withdraw consent at any time during the project. If there are measurements, eg performance tests, which the participants do not want to participate in, available data is collected from the journaling system (CURA) without participation in all measurements.

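### The claim of at least 80% power for any SD up to 1.87 fails: that limit assumes no clustering and 20 residents per home, but about 100 residents (16.7 per home) are planned

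*Protocol*

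**What the plan says.** The sample size paragraph in section 3a of the protocol starts from six nursing homes, about 20 willing overweight or obese residents in each, a detectable change of 1.3 on the 30-second chair stand test, a 5% significance level and 80% power. Section 3c gives three homes per arm. The paragraph introduces its calculation with "Initially the power calculation is performed by the individual randomization", but the key quantity is at home level: "the standardized difference in the nursing center incl. intra cluster correlation, SD diff, nursing center = 0.42". It then equates this home-level SD with the person-level SD divided by the square root of n, obtains about 1.87 for the person, and concludes: "If SD is 1.87 or less, the power will be at least 80% or greater".

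Two caveats follow: "if there are fewer than 20 people power will decrease" and "After sub study 1 a more accurate number can be provide". The next paragraph plans for fewer than 20 per home: "Approximately 100 participants will be included and cluster randomized". Section 3b repeats the total: "estimated 100 older adults is expected to be enrolled in the project". No ICC and no expected SD are stated.

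**The concern.** There are two faults in the step from 0.42 to 1.87.

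- **Clustering is dropped.** The 0.42 is described as including the intra-cluster correlation. Dividing a person-level SD by the square root of n gives the SD of a home mean only when residents within a home are uncorrelated. Any between-home variation that 0.42 was meant to hold is lost in the conversion.
- **The cluster size does not match the plan.** The conversion uses 20 per home, which is 6 × 20 = 120 participants. The planned total is about 100, or 100/6 = 16.7 per home. The paragraph says that fewer than 20 lowers power but leaves the limit of 1.87 unchanged.

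The practical risk lies in how the limit would be used. If sub-study 1 yields an SD between the correct limit and 1.87, the team would conclude that power is at least 80% when it is not. The chair stand test is part of the primary outcome. Putting a new SD into the same formula would repeat the error.

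**Working it through.** **Inputs from the protocol.** Difference 1.3; significance level 0.05 (two-sided assumed, as sidedness is not stated); power 80%; three homes per arm; 20 residents per home in the calculation; home-level SD 0.42; person-level limit 1.87; planned total about 100.

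**Assumed.** ICC values of 0.01 to 0.10, and equal home sizes.

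**Step 1: reproduce the protocol's figures.** Take a t-test on home means, 3 versus 3, with 4 degrees of freedom and noncentrality 1.3/(SD_home × √(2/3)).

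- At SD_home = 0.42 the noncentrality is 1.3/(0.42 × 0.8165) = 3.79, and power is 80.6%. Power is exactly 80% at SD_home = 0.4233.
- 0.42 × √20 = 1.878, which matches the stated 1.87.
- Other methods do not give 0.42: a one-sided t-test gives 0.524, a normal approximation 0.568, three matched pairs 0.398. Individual randomisation at SD 1.87 would need only 33 per arm. The calculation is therefore a home-level one, whatever its label.

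**Step 2: planned cluster size, still at ICC 0.** SD_home = 1.87/√16.67 = 0.458, and power is 73.9%, against 80.9% with 20 per home. The largest person-level SD that keeps 80% is 0.4233 × √16.67 = 1.73.

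**Step 3: restore the ICC.** The SD of a home mean is SD_home = SD_person × √((1 + (n − 1) × ICC)/n). The same t-test then gives, at SD_person = 1.87:

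| ICC | Power, n = 20 | Power, n = 16.7 | SD limit for 80%, n = 16.7 | Detectable difference at 80%, n = 16.7 |
|---|---|---|---|---|
| 0 | 80.9% | 73.9% | 1.73 | 1.41 |
| 0.01 | 74.3% | 68.0% | 1.61 | 1.51 |
| 0.05 | 54.3% | 50.7% | 1.29 | 1.88 |
| 0.10 | 40.1% | 38.3% | 1.08 | 2.25 |

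The SD limit is 0.4233/√((1 + (n − 1) × ICC)/n). The detectable difference is 1.3 × SD_home/0.4233.

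**Step 4: how much clustering can be tolerated.** The largest ICC that keeps 80% is (0.4233² × n/SD² − 1)/(n − 1).

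- SD 1.87, n = 20: (3.584/3.497 − 1)/19 = 0.0013.
- SD 1.87, n = 16.7: negative, so no ICC qualifies.
- SD 1.5, n = 16.7: 0.021.
- SD 1.3, n = 16.7: 0.049.

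**Step 5: the favourable case.** At SD 1.5 and 16.7 per home, power is 89% (ICC 0), 85% (0.01), 80% (0.02) and 68% (0.05).

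**Step 6: another reading of 1.87.** If 1.87 is taken as the within-home SD, power at n = 20 is 73.9% (ICC 0.01) and 52.3% (ICC 0.05), so this reading does not rescue the statement.

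**The case against.** Read as a whole, the paragraph offers a provisional planning value. The limit follows from 20 per home, the text says that smaller homes lower power, and it expects a better figure after sub-study 1. The total of 100 is approximate, inclusion is ongoing, and at ICC 0 the loss from 20 to 16.7 per home is 7 points (80.9% to 73.9%). The larger losses rest on ICCs that the protocol does not give. The t-test on 4 degrees of freedom is inferred from the match with 0.42, and section 4 plans a covariate-adjusted ANCOVA, whose power may differ. This is a feasibility study with a fixed set of six homes.

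Much of this is fair, and it limits the weight of the point. The 68%, 51% and 38% figures are illustrations. The individual-randomisation label is a wording fault that misleads nobody about the design. None of it makes the statement correct: the caveat on home size is not applied to the protocol's own 100, and neither caveat touches the missing ICC.

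One objection bears on the remedy. The SD in the formula appears to be that of a change, whereas section 2b describes sub-study 1 as a characterisation under the screening model. Nothing shown says that it will yield an SD or ICC of change, and an ICC estimated from six homes would be imprecise.

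**Conclusion.** The statement is wrong as written and should be corrected. From the protocol's own numbers, with the inferred two-sided test on home means and no assumed ICC, the limit for 80% power at 100 participants is 1.73 rather than 1.87, and power at 1.87 is 73.9%. Even at 20 per home, SD 1.87 keeps 80% only up to an ICC of about 0.001. Any larger ICC lowers the limit further, by an amount that depends on assumption.

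This does not show that the trial is underpowered. The 1.87 is an upper limit, not an expected SD, and a true SD near 1.5 with an ICC up to about 0.02 would still give 80%.

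**What to change.** Rewrite the sample size paragraph in section 3a:

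1. Keep the home-level threshold (SD 0.42, three versus three homes), name the test behind it, and remove the reference to individual randomisation.
2. Replace the conversion with SD_home = SD_person × √((1 + (n − 1) × ICC)/n).
3. Set n at about 16.7, less the chair stand tests expected to be missing, because section 12 allows tests to be declined: "If there are measurements, eg performance tests, which the participants do not want to participate in, available data is collected". Alternatively, reconcile the total of 100 with 6 × 20 = 120.
4. Take the SD and ICC from sub-study 1 if it provides them for the same quantity; otherwise show a range of ICCs.
5. State the resulting SD limit, power or detectable difference, and delete the assurance based on 1.87.

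The cost is one paragraph. Homes, participants and outcomes stay as they are; the stated power becomes less favourable.
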